10.5 For phase 2 protocols only: Reporting and Exclusions

10.5.1 Evaluation of Toxicity

All patients will be evaluable for toxicity from the time of their first treatment with Pembrolizumab (MK-3475).

Severe pembrolizumab-related toxicity is defined as the occurrence of any of the below AEs that are attributed to pembrolizumab. The evaluability period includes the first 35 days after pembrolizumab first dose, till hematologic recovery, or till starting consolidation therapy, whichever occurs first.

10.5.1.1 Any grade 3 or 4 non-hematologic toxicity, that is deemed related to Pembrolizumab (MK-3475), with the following exceptions: A) Transient laboratory abnormalities that can be treated or resolve to grade 2 or less within 7 days. B) grade 3 expected and known drug-related autoimmune events (such as pneumonitis, enterocolitis, hepatitis, hypophysitis, and skin rash) that resolve within 4 weeks of steroid therapy to grade 1.

10.5.1.2 Grade 4 thrombocytopenia or neutropenia associated with treatment-associated aplasia lasting >42 days from the last dose of study drug (pembrolizumab). Given that severe neutropenia and thrombocytopenia are features of AML and commonly encountered in this patient population, they will not be used to define unacceptable toxicity except if associated with prolonged treatment-associated aplasia AND not associated with active disease.

10.5.1.1.3 Patients with grade 3 and 4 immune related AEs (with exception of events that resolve with steroids to grade 1 or less and do not require continued steroid therapy beyond 4 weeks).

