1.2 Secondary Objectives

- 1.2.1 Assess the rate of complete remission (CR) / complete remission with incomplete count recovery (CRi) as defined per European Leukemia Net 2017 response criteria at time of count recovery after induction therapy with chemotherapy + Pembrolizumab (MK-3475) (Dohner *et al.*, 2017).
- 1.2.2 Rates of complete remission with partial recovery count (CRh) and Hematologic improvement (HI) to red blood cells and platelets
- 1.2.3 Assess the rates of MRD negativity at Day 14, MRD-negative CR at end of induction therapy and MRD negative CR after last consolidation cycle.
- 1.2.4 Assess event free survival (EFS), measured from randomization to failure to achieve CR/CRi, relapse or death from any cause, and relapse free survival (RFS), calculated as the time from first documentation of CR/CRi to either disease relapse or death from any cause.
- 1.2.5 Assess the duration of response (DOR, defined as the time from first CR/CRi to the date of the first documented relapse or death, whichever occurs first) and overall survival (OS), defined as time from randomization to death from any cause.
- 1.2.6 Assess safety endpoints including proportion of patients who develop severe toxicity as defined in the protocol.

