7.1.1 Induction therapy phase

Eligible patients will be randomized before proceeding to 7+3, or within one week of starting 7+3 in 1:1 ratio, to 7+3 alone or 7+3+ Pembrolizumab (MK-3475). As shipment of pembrolizumab to site can only be ordered after randomization, every effort should be done to randomize the patient as soon as possible. See Section 9.1 for agent ordering information. If patient is randomized after initiation of 7+3 therapy, the patient should continue to meet all eligibility criteria up to randomization date. Planned stratification factors include 1) age (younger than 65 vs. 65 and older), 2) cytogenetics **by FISH or metaphase karyotype** (presence vs. absence of core binding factor inversions and translocations), and 3) **t- AML or AML arising from prior/antecedent MDS (yes/no)**. All patients will receive cytarabine at 100 mg/m²/day continuous infusion on Days 1-7 and either idarubicin 12 mg/m²/day IV on Days 1-3 or daunorubicin 60 mg/m²/day IV on Days 1-3. A bone marrow biopsy on Day 14 (between Days 14 and 21) will be performed to assess for chemoablation. If patients have evidence of residual leukemia (defined as per institutional practice) in their bone marrow and following assessment by repeat transthoracic echocardiography (TTE) for assessment of ejection fraction, they will receive re-induction 5+2 chemotherapy, which means patients will receive cytarabine at 100 mg/m²/day continuous infusion on Days 1-5 and either idarubicin 12 mg/m²/day IV or daunorubicin 60 mg/m²/day IV on Days 1-2. Anthracycline dosing adjustments may need to be made, per institutional guidelines. Regardless of chemoablation status, on Day 8 of the induction chemotherapy and Q3W (±3 days) thereafter, half of the patients will receive Pembrolizumab (MK-3475) IV (intervention arm). The other half will not receive Pembrolizumab (MK-3475) (control arm). At time of count recovery, defined as platelet count more than 50,000 or neutrophil count more than 500, patients will undergo a bone marrow aspirate/biopsy in order to assess for response and MRD. If there is no count recovery, a bone marrow will have to be performed by day 42. If the bone marrow shows hypoplasia and patient remains without count recovery, a bone marrow will be performed q 2 weeks (+/- 3 days) till there is count recovery or evidence of persistent AML. If patients have a CR or a CRi, patients will continue with consolidation therapy. If patients do not achieve a CR or CRi, they will be taken off study. If Pembrolizumab is discontinued for any reason (after at least one dose of Pembrolizumab, the patient should continue on 7+3 or Re-Induction on study.

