10.4 Analysis of Secondary and Exploratory Endpoints

10.4.1 Secondary Endpoints

10.4.1.1 Efficacy Endpoints:

- Assess the rate of CR/CRi as defined per the ELN 2017 (see Appendix D) response criteria at time of count recovery after induction therapy with chemotherapy + Pembrolizumab (MK-3475).
- Assess MRD negativity at Day 14.
- Assess the rate of MRD-negative CR at end of induction therapy.
- Assess the rate of MRD-negative CR at end of consolidation.
- Assess rates of complete remission with partial recovery count (CRh) and Hematologic improvement (HI) to red blood cells and platelets.
- Assess the percentage of patients with MRD-CR at time of count recovery after first cycle of consolidation therapy using a MRD cut-off of 0.01%.
- Assess EFS, RFS, calculated as the time from initial treatment to either disease relapse or death.
- Assess the DOR (defined as the time from first CR to the date of the first documented relapse or death, whichever occurs first) and OS.

10.4.1.2 Safety Endpoints:

- Assess safety endpoints including proportion of patients who develop severe toxicity.

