13.1 Definitions

Evaluable for toxicity. All patients will be evaluable for toxicity from the time of their first treatment with 7+3 with or without Pembrolizumab (MK-3475)

Evaluable for objective response. Only those patients who have measurable disease present at baseline, have received at least one cycle of therapy, and have had their disease reevaluated will be considered evaluable for response. These patients will have their response classified according to the definitions stated below. (Note: Patients who exhibit objective disease progression prior to the end of Cycle 1 will also be considered evaluable). All patients starting induction therapy should be included in the primary analysis with drop-outs considered as not being MRD- for the analysis of rates.

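### The only severe-toxicity definition needs pembrolizumab attribution and timing, so endpoint 1.2.6 is zero or undefined in controls, and Sections 10.5.1 and 13.1 disagree on who is evaluable

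*Combined protocol and SAP*

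**What the plan says.** Two sections define who is evaluable for toxicity.

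- Section 10.5.1: "All patients will be evaluable for toxicity from the time of their first treatment with Pembrolizumab (MK-3475".
- Section 13.1: "All patients will be evaluable for toxicity from the time of their first treatment with 7+3 with or without Pembrolizumab (MK-3475".

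The secondary safety objective, 1.2.6, reads "Assess safety endpoints including proportion of patients who develop severe toxicity as defined in the protocol". Section 10.4.1.2 repeats it as "Assess safety endpoints including proportion of patients who develop severe toxicity" and names no contrast or method.

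The one definition available is in Section 10.5.1: "Severe pembrolizumab-related toxicity is defined as the occurrence of any of the below AEs that are attributed to pembrolizumab". Its timing is "The evaluability period includes the first 35 days after pembrolizumab first dose, till hematologic recovery, or till starting consolidation therapy, whichever occurs first". The qualifying events are grade 3 or 4 non-hematologic toxicity with exceptions (10.5.1.1), prolonged treatment-associated aplasia (10.5.1.2), and grade 3 and 4 immune-related events with exceptions (numbered 10.5.1.1.3).

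On control treatment, Section 7.1.1 says "The other half will not receive Pembrolizumab (MK-3475) (control arm".

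Section 10.1 uses the attributed definition for an early rule: enrollment is held if two or more of the first six evaluable pembrolizumab-arm patients have severe pembrolizumab-related toxicity. It also schedules a formal toxicity analysis once each arm has 25 efficacy-evaluable patients, without giving its measure, window or method.

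**The concern.** The two evaluability statements cannot both govern. Under Section 10.5.1 no control patient is ever evaluable, and a pembrolizumab-arm patient who leaves before the first dose is not evaluable either. Under Section 13.1 both are.

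Choosing Section 13.1 does not repair the endpoint, because it supplies a population and not a measure. The definition that 1.2.6 points to still needs an event attributed to a drug that controls do not receive, in a period that starts with a dose they do not get.

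At stake is the reading of safety in a randomised, open-label trial. If the endpoint is reported as written, one arm has a number and the other has a structural zero or a blank. If no treatment-neutral measure is fixed in advance, the measure for the formal toxicity analysis will be chosen after open-label data have been seen.

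The grade wording raises a separate gap. Deaths are graded 5 elsewhere in the protocol (Section 11.3.3), but the non-hematologic and immune criteria stop at grade 4.

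**Working it through.** **1. The plan's own figures.** The attributed definition feeds the 2-of-6 rule, for which P(X ≥ 2) = 1 − (1−p)^6 − 6p(1−p)^5.

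- p = 0.50: 1 − 1/64 − 6/64 = 57/64 = 0.891 (Section 10.1 states at least 0.89).
- p = 1/3: 1 − 64/729 − 192/729 = 473/729 = 0.649 (stated 0.65).

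Both reproduce. The definition fits the single-arm rule it serves.

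**2. The same definition applied to a control patient.**

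- Attribution: it cannot be met, because no pembrolizumab is given.
- Window: it has no start date, because its origin is the first pembrolizumab dose.
- Population: not evaluable under Section 10.5.1, evaluable under Section 13.1.

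The control proportion is therefore 0/0 under Section 10.5.1 and 0/25 under Section 13.1, whatever the true toxicity.

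**3. Coverage in the pembrolizumab arm.** The window closes no later than the start of consolidation. Events in up to four consolidation cycles and up to 2 years of maintenance (Sections 7.1.2 and 7.1.3) fall outside it. Read literally, the aplasia criterion needs more than 42 days from the last dose, while the window ends by 35 days from the first. Since the last dose cannot precede the first and 42 > 35, that criterion cannot be established inside the window.

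**4. Fatal events.** Suppose that, among the first six, one patient dies of a pembrolizumab-related non-hematologic event and one other has a qualifying grade 3 event. The literal count is 1, below the threshold of 2.

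**5. What a forced zero would do if the arms were contrasted.** The one-sided Fisher p-value for x/25 against 0/25 is C(25,x)/C(50,x).

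- x = 3: 2300/19600 = 0.117.
- x = 4: 12650/230300 = 0.055.
- x = 5: 53130/2118760 = 0.025.

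A handful of attributed events would look like an excess even if all-cause toxicity were equal. The documents give no attribution fraction, so I do not size how often this would happen.

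**6. Precision of an all-cause comparison.** With 25 per arm and equal rates p (assumed, not in the documents), the 95% half-width for the difference is 1.96 × √(2p(1−p)/25).

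| p | Half-width (points) |
|---|---|
| 0.20 | 22.2 |
| 0.30 | 25.4 |
| 0.40 | 27.2 |
| 0.50 | 27.7 |

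**The case against.** A reader might infer that toxicity is evaluable only from first pembrolizumab throughout the protocol, and that safety cannot be compared between arms at all. The documents do not support this. Section 13.1 makes controls evaluable. Section 11.3.1 collects all post-baseline adverse events, Section 11.4 requires all to be reported, and Section 7.4 monitors post-transplant events in both arms. Objective 1.2.6 also presents the proportion as one item among the safety endpoints.

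Nor does the plan promise a between-arm test of this proportion. The primary objective says the arms will be compared; 1.2.6 and 10.4.1.2 only say assess. For the early rule, which requires at least one pembrolizumab dose, leaving out controls and patients lost before Day 8 is coherent. This stands, and it limits the point to the named endpoint and the undefined formal analysis.

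A reader might also try to size the bias from the febrile neutropenia rate tabulated in Section 11.1.3. That fails. The study was single-arm and every patient was to receive a checkpoint inhibitor, so the rate is not a checkpoint-free background. It is not shown that febrile neutropenia would qualify under Section 10.5.1, and any attribution fraction would be invented.

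On fatal events, expedited reporting of deaths, the safety review committee and the DSMB all offer protection. The gap is in how the rule counts, not in whether deaths would be noticed.

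Finally, counting from first 7+3 has its own flaw. Section 7.1.1 allows randomisation up to a week after 7+3 starts, so that origin can include pre-randomisation time. The fix has to avoid this.

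**Conclusion.** Wrong as written, on three counts. Sections 10.5.1 and 13.1 contradict each other on the toxicity-evaluable population and its starting point. The only definition behind 1.2.6 is zero or undefined in controls and cannot support a between-arm safety contrast. Its non-hematologic and immune criteria literally omit fatal events, from both the endpoint and the 2-of-6 rule.

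These conclusions follow from the text and need no assumed rates. The early safety rule's stated probabilities are correct, and its use of an attributed definition is sound. The data for a comparison exist; what is missing is the measure, window and method. The size of any spurious excess cannot be derived from the documents. The half-widths rest on 25 evaluable patients per arm, equal rates of 20% to 50% and a normal approximation.

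**What to change.** - Reconcile Sections 10.5.1 and 13.1. For 1.2.6 and the formal toxicity analysis, use the Section 13.1 population: all treated patients in both arms. State the arm in which patients who leave before a first pembrolizumab dose are counted; keeping them in their randomised arm preserves the contrast.
- Report grade 3 to 5 adverse events regardless of attribution, by arm and treatment phase. Tabulate hematologic and non-hematologic events separately, because Section 2.3.1.3 expects severe pancytopenia in all patients. Report prolonged aplasia as its own item, over a window long enough to observe it.
- Use the same windows in both arms from an origin that excludes pre-randomisation time: the later of randomisation and first 7+3, or a common Day 8 landmark.
- Keep the pembrolizumab-attributed definition for the early safety rule only, and state there how fatal events count.
- Present differences with 95% confidence intervals.

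The cost is analysis wording: no new patients, procedures or data. Two limits remain. The comparison is imprecise at this sample size. Maintenance-phase results also need a caveat. By the Section 12 footnotes, blood counts and chemistry accompany each three-weekly pembrolizumab dose but are six-weekly in control-arm observation, where visits may also be six weeks apart. Detection would therefore be higher in the pembrolizumab arm, and wording cannot remove that.

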toxicity data to identify any concerning drug-related safety signals before enrolling further patients on the experimental arm. We will temporarily hold enrollment in the study if two or more patients of the first evaluable six patients in pembrolizumab (MK-3475) arm develop pembrolizumab-related severe toxicity during evaluability period. The evaluability period includes the first 35 days after pembrolizumab first dose, till hematologic recovery, or till starting consolidation therapy, whichever occurs first, as defined in section 9.5.1. To be considered evaluable for purposes of the early safety rule, the patient must have received at least one pembrolizumab dose. If the true toxicity rate is 50% or greater, this rule will stop the trial with probability at least 0.89. Similarly, if the true toxicity rate is 33%, this stopping rule will end the trial with probability 0.65. In the event this occurs, the study would resume with another 6-patient cohort in which pembrolizumab dosing will start on Day 21 instead of Day 8. The patient has to receive at least one dose of pembrolizumab to be considered evaluable for safety assessment for purposes of early stopping safety rule. If the altered schedule still results in unacceptable toxicity, we will discuss alternative approaches with CTEP. No enrollment may take place until this discussion has occurred and a suitable plan has been developed.

Toxicity analysis: The first six enrolled patients will be assessed for severe toxicity in the pembrolizumab arm. In the event that severe toxicity occurs in 2 or more of the first 6 patients, the study would resume with another 6-patient cohort in which pembrolizumab dosing will start on Day 21 instead of Day 8. If the altered schedule still results in unacceptable toxicity, we will discuss alternative approaches with CTEP. A formal toxicity analysis will be conducted after 25 efficacy-evaluable patients in each study arm.

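### The formal 2-of-6 hold count leaves out attributed events recorded only as grade 5, and its aplasia criterion cannot be completed inside the 35-day evaluability period

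*Combined protocol and SAP*

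**What the plan says.** Section 10.1 (Early safety schedule change) sets the rule: "We will temporarily hold enrollment in the study if two or more patients of the first evaluable six patients in pembrolizumab (MK-3475) arm develop" severe toxicity related to pembrolizumab within the evaluability period. It gives hold probabilities of at least 0.89 at a true rate of 50% or more, and 0.65 at 33%. After a hold, the study resumes with another six-patient cohort and a later pembrolizumab start.

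Section 10.1 cites 9.5.1 for the period. The matching text stands in 10.5.1: "The evaluability period includes the first 35 days after pembrolizumab first dose, till hematologic recovery, or till starting consolidation therapy, whichever occurs first". Section 10.5.1 then lists three criteria.

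- **10.5.1.1:** "Any grade 3 or 4 non-hematologic toxicity, that is deemed related to Pembrolizumab (MK-3475"), with exceptions for short-lived laboratory abnormalities (exception A) and for expected grade 3 autoimmune events "that resolve within 4 weeks of steroid therapy to grade 1" (exception B).
- **10.5.1.2, the aplasia criterion:** "Grade 4 thrombocytopenia or neutropenia associated with treatment-associated aplasia lasting >42 days from the last dose of study drug (pembrolizumab"). Other severe neutropenia or thrombocytopenia is set aside, so this is the only hematologic route into the count.
- **10.5.1.1.3, the immune-related criterion:** "Patients with grade 3 and 4 immune related AEs (with exception of events that resolve with steroids to grade 1 or less" and need no steroids after four weeks).

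On dosing, Section 7.1.1 starts pembrolizumab on induction Day 8 and repeats it every three weeks (±3 days). Section 8.1.4 does not in general withhold it for cytopenia during induction or consolidation, unless it is thought to cause or contribute to the cytopenia.

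**The concern.** The 2-of-6 count is the only quantified part of the early safety review. It decides whether enrollment is held and the altered-schedule cohort opened, so what counts as an event should be unambiguous before the sixth patient is scored. Two features work against that.

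First, the worst grade is missing from two of the three criteria. A pembrolizumab-attributed event that appears in the data only as grade 5 meets neither the non-hematologic nor the immune-related wording.

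Second, the aplasia criterion and the window run on different clocks. One counts forward from the last dose, the other from the first, and the criterion is longer than the window. Two people scoring the same patient with prolonged aplasia could reach different answers, and the rule could turn on that patient.

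**Working it through.** **1. The plan's own figures.** With X the number of countable events among six patients and p the true rate, P(hold) = P(X ≥ 2) = 1 − (1−p)^6 − 6p(1−p)^5.
- p = 0.5: 1 − 7/64 = 57/64 = 0.891 (stated: at least 0.89).
- p = 1/3: 1 − 256/729 = 473/729 = 0.649 (stated: 0.65).

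Both reproduce. The arithmetic is sound; the question is which events enter X.

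**2. Grades.** Sections 10.5.1.1 and 10.5.1.1.3 name grades 3 and 4. Elsewhere the protocol writes thresholds differently. Section 8.1.4 uses an open-ended grade 3 or higher for withholding pembrolizumab for non-hematologic toxicity. Section 11.3.3 names grade 5 next to grade 4 in its reporting times. Set side by side, these do not support reading the 10.5.1 wording as shorthand that takes in grade 5. An event also recorded at grade 3 or 4 before death can still be counted; the gap is the event recorded only as grade 5.

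**3. Aplasia timing.** Let day 0 be the first pembrolizumab dose. The window ends by day 35. The criterion needs more than 42 days from the last dose, so the earliest completion day is (day of last dose) + 43.

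| Last dose given | Day of last dose | Earliest completion | Days past day 35 |
|---|---|---|---|
| First | 0 | 43 | 8 |
| Second | 21 (18–24) | 64 (61–67) | 29 (26–32) |
| Third | about 42 | about 85 | about 50 |

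The last dose cannot precede the first, so no dosing pattern completes the criterion by day 35. The second row holds only if dosing stops after dose two. While three-weekly dosing continues the clock keeps restarting, and Section 8.1.4 generally lets dosing continue through cytopenia in induction. Both clocks run from pembrolizumab dosing, so the cohort with the later start would have the same mismatch.

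**4. Steroid exceptions.** These allow up to four weeks for resolution. Since 35 − 28 = 7, an event whose steroids start after day 7 may still be unresolved, with its four weeks not yet over, when the window closes. On a plain reading an unresolved event counts, which favours a hold, but the plan does not say whether the decision waits.

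**The case against.** The strongest reply is that the count is not the only protection. Section 10.1 also has a committee review the "toxicity data to identify any concerning drug-related safety signals before enrolling further patients on the experimental arm". Section 11.3.3 requires expedited reporting of deaths within 30 days of the last dose of investigational agent, and of attributed serious events after that. Section 10.6 gives the DSMB a role in possible closure. A reader might infer from the missing grade 5 that a drug-related death would go unnoticed or that enrollment would simply continue. The documents do not support that. This reply stands, and it limits the harm, but these safeguards rest on judgment and do not change what the formal count includes.

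On aplasia, the verb that closes the quoted hold rule in Section 10.1 permits an onset reading: aplasia that starts in the window counts, and its duration is established later. Section 7.1.1 repeats marrows about every two weeks when counts have not recovered, so data would exist. A reader might therefore go too far in saying that aplasia can never count. What stands against the plan is narrower: no section states the onset reading or says that the six-patient decision waits. The Toxicity analysis paragraph ("The first six enrolled patients will be assessed for severe toxicity in the pembrolizumab arm") restates the rule with no window, so it does not settle the matter. Its different term for the six patients is not a further defect, because Section 10.1 already says that evaluable means at least one pembrolizumab dose.

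A reader might also infer that the true hold probabilities lie well below 0.89 and 0.65. That would need the share of severe events that escape the definition. The documents give none, and a figure that assumes such an event has already occurred would overstate the effect.

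**Conclusion.** Both points hold, as defects of definition. Read literally, the count excludes pembrolizumab-attributed non-hematologic and immune-related events recorded only as grade 5. The aplasia criterion cannot be completed inside its own window: the shortfall is 8 days with one dose, about 29 days (26–32) if dosing stops after two, and more with each further dose. It becomes scorable only under an onset reading that the plan does not state.

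The stated 0.89 and 0.65 are correct for events the definition can count, and no size of effect on them is claimed. The conclusion rests on the literal wording of 10.5.1, on the three-weekly schedule in 7.1.1, and on 10.5.1 being the section meant by the reference to 9.5.1. It should be fixed: the only quantified early safety trigger omits the most severe grade and contains a criterion that cannot be met in its window.

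**What to change.** Wording changes only; no change to the 2-of-6 threshold, the dose or the schedule is proposed.

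1. In 10.5.1.1 and 10.5.1.1.3, word the criteria so that the formal count does not exclude pembrolizumab-attributed grade 5 events.
2. Reconcile 10.5.1.2 with the evaluability period in 10.1 and 10.5.1. State whether onset or completion of aplasia counts, which dose starts the clock if three-weekly dosing continues, and whether the six-patient decision waits for ascertainment, including steroid exceptions still pending. The sponsor chooses the figures.

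The cost is possible delay. If the decision must wait for the aplasia criterion to be completed or ruled out, it comes at least 8 days after the window with one dose and later with further doses, in cases where one of the six is still aplastic at day 35. Waiting for pending steroid exceptions could add more. Because the committee review precedes further enrollment on the experimental arm, such a wait would lengthen that pause.
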